5.3 Exclusion criteria

A potential subject who meets any of the following criteria will be excluded from participation in this study:

- Children born with congenital and/or chromosomal abnormalities.
- Children that passed away before inclusion.

5.4 Sample size calculation

Of note, performing sample size calculations in the context of this rare disease is difficult since literature is scarce and heterogeneous.

We performed two different sample size calculations for the two cohorts.

Cohort 1: Using the literature to date we estimated that the IQ score of FNAIT survivors without antenatal treatment is lower, that is 92 versus average (100) in the normal population. To show a difference in IQ score between FNAIT survivors without IVIg treatment compared to a fixed average of 100, we performed a sample size calculation for a one-sample t-test. We calculated that a minimum group size of 39 was needed to show a mean difference of 7 IQ points with a power of 0.8 and a significance of 0.05. We assume a standard deviation (SD) of 15 for the IQ score.

Cohort 2: In the FNAIT survivors with antenatal treatment we expect no difference in IQ score between cases and the national average. To show that there is no difference IQ score in anticipated IVIg treatment compared to the Dutch average we perform a non-inferiority calculation by a one-sample t-test. In this case we need a sample size of 39 children with a non-inferiority margin of 7 IQ points, with a power of 0.8 and a significance level of 0.025. We assume a standard deviation (SD) of 15 for the IQ score.

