3. OBJECTIVES

3.1 Primary objective(s)

The primary objective is to determine the cognitive test score of children diagnosed with FNAIT without and with antenatal treatment. We will assess the neurodevelopmental outcome, with IQ score as outcome measure, of two groups:

Cohort 1: To evaluate the natural history of FNAIT, we will include in this first cohort all FNAIT survivors without antenatal treatment. Our hypothesis is that the cognitive test score in this cohort will be lower compared to the general population.

Cohort 2: To evaluate the safety and benefit of IVIg treatment, the IQ score in all FNAIT survivors treated with antenatal IVIg treatment will be determined. Our hypothesis is that the cognitive test score in this cohort is similar to the general population.

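### Success in cohort 2 would exclude a mean deficit of 7 IQ points or more, but the plan words the aim as no difference and similarity to the population

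*Combined protocol and SAP*

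**What the plan says.** Section 5.4 (Sample size calculation) treats the two cohorts in turn.

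- **Cohort 1, untreated.** The expected mean IQ is given as "that is 92 versus average (100) in the normal population", a deficit of 8. The calculation then finds that "a minimum group size of 39 was needed to show a mean difference of 7 IQ points", with power 0.8 and significance 0.05.
- **Cohort 2, IVIg-treated.** The assumption is that "we expect no difference in IQ score between cases and the national average". The stated purpose is to show that no difference exists, by a one-sample non-inferiority test: "In this case we need a sample size of 39 children with a non-inferiority margin of 7 IQ points". Power is again set at 0.8, and the level at 0.025.
- **Both cohorts.** "We assume a standard deviation (SD) of 15 for the IQ score".

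Section 3.1 says that cohort 2 is there to evaluate the safety and benefit of IVIg. Its hypothesis reads: "Our hypothesis is that the cognitive test score in this cohort is similar to the general population".

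Section 11 compares both cohorts with the Dutch average by linear regression. It mentions no margin, confidence interval or decision rule. No section gives a clinical or statistical reason for choosing 7 points.

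**The concern.** A non-inferiority test supports one statement: the deficit is smaller than the margin. Whether that amounts to being similar depends on how small the margin is. Here it equals the difference that the companion cohort is designed to find, and it stops one point short of the deficit expected without treatment. Cohort 2 could therefore pass with a true mean several points below 100, and the plan's wording would turn that pass into similarity with the population. The introduction says that these results matter for counselling parents and that the long-term safety of IVIg in this disease has not been evaluated. An overstated conclusion would carry weight there.

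**Working it through.** **Inputs, all from section 5.4:** SD 15; margin 7, so the non-inferiority limit is 100 − 7 = 93; assumed true difference 0; power 0.8; significance 0.025, taken as one-sided because the section does not state sidedness; n = 39; expected untreated mean 92.

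**1. Reproduce the plan's figure.** The normal approximation is n = [(1.960 + 0.842) × 15/7]² = 36.04, so 37. The exact one-sample t-test (noncentral t) needs n = 39, with power 0.811. Cohort 1, with a difference of 7 and two-sided 0.05, also gives 39 with power 0.811. The stated sample sizes are right.

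**2. Place the margin against the plan's other figures.**
- Margin / cohort 1 target difference = 7/7 = 1.
- Margin / expected untreated deficit = 7/8 = 0.875.
- Non-inferiority limit minus expected untreated mean = 93 − 92 = 1 point.

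**3. What must be observed to pass at n = 39.** SE = 15/√39 = 2.402. The half-width of the 95% interval is 2.024 × 2.402 = 4.86. The observed mean must therefore exceed 93 + 4.86 = 97.86. An observed mean of 96 has the interval 91.1 to 100.9 and fails.

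**4. Chance of declaring non-inferiority.** For true mean μ this is P(T > t₀.₉₇₅,ₙ₋₁), where T is noncentral t with n − 1 degrees of freedom and noncentrality (μ − 93)√n/15. For μ = 96 and n = 39 the noncentrality is 3 × 6.245/15 = 1.249.

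| True mean | Deficit | Chance at n = 39 |
|---|---|---|
| 100 | 0 | 0.81 |
| 98 | 2 | 0.53 |
| 96.5 | 3.5 | 0.29 |
| 96 | 4 | 0.23 |
| 95 | 5 | 0.13 |
| 93 | 7 | 0.025 |
| 92 | 8 | 0.009 |

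**5. Dependence on n.** At a true mean of 96 the chance is 0.51 at n = 100 and 0.80 at n = 200. Both sizes are illustrations. The documents invite all eligible children but give no expected cohort 2 number above 39.

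**6. Can the interval lie wholly between 93 and 100?** At n = 39 and an observed SD of 15, the interval is 2 × 4.86 = 9.72 points wide, which exceeds 7, so it cannot. It would need an observed SD below about 15 × 7/9.72 = 10.8. By simulation, at a true mean of 96.5, the probability is about 0.0003 to 0.0004. With SD 15 the interval narrows to 7 points at about n = 73.

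**The case against.** The best defence is that the planned test is fairly demanding. At 39 children the observed mean must be about 97.9. A true mean of 96 fails in about 77% of studies, and a cohort at the expected untreated mean of 92 passes in about 1%. The margin also lies below the expected deficit of 8, so success does exclude a deficit as large as the untreated one. Section 5.4 is open about the rarity of the disease and the thin literature, which may justify sizing at 7. All of this stands. It defends the size of the test, but it does not justify reading a pass as similarity.

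A reader might infer more than the documents support:

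- **That section 5.4 contradicts itself, by treating 7 points as harmful in one cohort and acceptable in the other.** It says neither. It speaks of a difference, and one number can serve both as a detectable difference and as a margin.
- **That a treated cohort retaining half of the untreated deficit would usually pass.** At n = 39 it passes in about 23% of studies. The phrase also assumes that cohort 2 would have averaged 92 without treatment, which the documents do not state. Cohort 2 is compared with the Dutch average, not with cohort 1.
- **That the data will often be both significantly below 100 and non-inferior.** Step 6 shows that this is almost impossible at 39. Section 5.4 calls 39 a minimum only for cohort 1. Larger cohorts are conceivable, because all eligible children are invited, but no number is given.
- **That the margin ought to be 4 points.** Nothing in the documents supports that value. With SD 15 it would have power 0.37 at n = 39 and would need 113 children for 0.80.

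**Conclusion.** The concern holds as a mismatch between the test and the conclusion drawn from it. The margin is unexplained. It equals the cohort 1 target difference and is 7/8 of the expected untreated deficit. A pass excludes a true mean of 93 or lower and nothing closer to 100, while sections 3.1 and 5.4 word the aim as similarity and no difference, and section 11 has no rule to limit the claim. At the planned size, a true 4-point deficit would be declared non-inferior about 23% of the time.

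These figures rest on SD 15, a fixed norm of 100, a one-sided 0.025 level and an unadjusted one-sample t-test. Taking 8 points as the benchmark uses the only effect size that the plan gives. The sample size of 39 is not in question.

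**What to change.** Keep 39 children and the 7-point test.

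1. **Sections 3.1 and 5.4.** Replace no difference and similar, as the conclusion of a successful test, with: *a mean deficit of 7 IQ points or more, the difference cohort 1 is sized to detect, is excluded.*
2. **Section 11.** State that the cohort 2 mean is reported with its two-sided 95% interval against 93 and 100, and that non-inferiority is declared only if the lower limit is above 93. State also that an interval wholly between 93 and 100 is reported as *lower than the population average, by less than 7 points*.

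The last rule will almost never apply at n = 39. It guards against an ambiguous result if many more children are enrolled.

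The cost is wording in three sections, with no extra children and no loss of power for the 7-point test. The downside is that the study may no longer conclude that treated children score similarly to the population. A tighter margin is not required.

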6. TREATMENT OF SUBJECTS

Not applicable.

7. INVESTIGATIONAL PRODUCT

Not applicable.

8. NON-INVESTIGATIONAL PRODUCT

Not applicable.

9. METHODS

9.1 Study parameters/endpoints

9.1.1 Main study parameter/endpoint

To determine the cognitive and motor development score in children diagnosed with FNAIT without and with antenatal treatment. This will be evaluated using formal neurologic examination [15] and Bayley scales of Infant and Toddler Development third edition (Bayley III) at 2-3 years,[16] Wechsler Preschool and Primary Scale of Intelligence third edition (WPPSI III) at 4 to 6 years,[17] and Wechsler Intelligence Scale for Children fifth edition (WISC V) at 7 to 16 years [18].

9.1.2 Secondary study parameters/endpoints

NDI is a composite outcome of:

- Cerebral palsy \geq grade II according to Gross Motor Classification System (GMFCS) [19]
- Impaired cognitive, language and/or motor development (test scores <70)
- Bilateral blindness and/or bilateral deafness
- Bilateral deafness requiring amplification

The Health Related Quality of life will be assessed with PedsQL and behavioral problem score will be assessed using the Child Behavior Checklist [20, 21].

Academic performance will be evaluated by obtaining test scores from the Dutch Pupil monitoring system. [14] The latest test scores from primary school will be requested. If children are in high school grades from grade 6 in primary school will be used in our evaluation to obtain uniform test scores. Three academic domains will be assessed; arithmetic and spelling performance and measurements on reading comprehension. Of these three domains the following scores will be obtained from the monitoring system; the raw test scores, standardized test scores and the level of the child.

To assess long-term effects of maternal IVIg treatment on the immune system of the child we will assess two outcome parameters:

- The prevalence of allergies, asthma and eczema will be evaluated by a questionnaire composed in collaboration with an allergist. The severity and control of the allergic rhinitis will be assessed by the CARATkids questionnaire [22].

- The prevalence of children with an abnormal incidence or frequency of infections will be assessed by a questionnaire based on the guideline; 'Richtlijn diagnostiek naar onderliggende aandoeningen bij kinderen met recidiverende luchtweginfecties' [23] and the 10 warning signs of PI of the Jeffrey Model Foundation. [24]

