2. INTRODUCTION AND RATIONALE

Fetal and neonatal alloimmune thrombocytopenia (FNAIT) is the most common cause of thrombocytopenia in otherwise healthy term-born neonates. [1] FNAIT is a rare disease with an incidence estimated around 1 per 1000 live newborns. [2] During pregnancy alloimmunization can occur due to incompatibility of the Human Platelet Antigens (HPA) on the maternal and fetal platelets. Alloimmunization and maternal production of antibodies directed against the HPA-positive fetal platelets, leads to thrombocytopenia and an increased risk of intracranial hemorrhages (ICH) in the fetus. Clinical presentation can vary from skin bleedings to severe ICH leading to lifelong neurologic sequelae or intrauterine death. [2] [3]

In the past, FNAIT was managed with invasive and high-risk interventions including intrauterine platelet transfusion (IUPT). Since the end of the 20th century, invasive intrauterine transfusions (IUT) were replaced by a new, non-invasive therapy: maternal administration of intravenous immunoglobulin (IVIg). This novel therapy resulted in a significant lower risk of intrauterine fetal death and ICH. [4] Intervention with immune modulation in the semi -allogenic environment of the fetus by administration of immunoglobulins (Ig) is successful, especially in preventing ICH. [5] However antenatal treatment with IVIg has been implemented as standard of care without strong methodological follow-up research of children from mothers treated with IVIg. To date, only two follow-up studies have been published in children with anticipated FNAIT cases. The first study of a FNAIT cohort treated with IVIg was done by Ward et al. in 2006. [6] They concluded that development of children treated for FNAIT was better compared to their non-treated siblings. Their conclusions were based on non-validated questionnaires taken by telephone, assessing the behavioral outcome of the children and were limited by a ~40% lost-to-follow-up rate. [6] A second follow-up study including 39 children was published by a research group from our center in 2004. This research stated that the outcome in children with FNAIT and exposed to maternal IVIg treatment was similar to the normal population. However, this study included a heterogenic group of children with different treatment strategies including IUT, hampering definitive conclusions and substantiating the need for more research. [7]

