3.2 Secondary Objective(s)

In both groups we will assess the incidence of neurodevelopmental impairment (NDI). NDI is a composite outcome including cerebral palsy (GMFCS \geq II), cognitive or motor test score of less than 70, hearing loss requiring amplification or visual impairment (legally certifiable as blind or partially sighted). Other secondary outcomes will be HRQoL and behavioral problem score. In both cohorts we will assess academic performance by evaluation of test scores on three domains; arithmetic and spelling performance and reading comprehension. [11-13]

We will also focus on potential long-term side effects of IVIg treatment and determine the prevalence of allergies, eczema, asthma and the course of infections.

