9.1.3 Other study parameters

An inventory will be made of the following confounders gender, obstetrical and neonatological complications and education level of the parents according to the International Classification of Education. [25] We will assess the family history of allergies asthma and eczema to obtain information about possible confounding factors in our study groups. Also smoking and day-care visit will be questioned.

Table 2: Overview assessments

Study assessments			
Age group	Name assessment tool	Abbreviation	Outcome
Cognitive development			
2-3 years	Bayley scales of infant and toddler development third edition.	Bayley III	IQ score
4-6 years	Wechsler Preschool and Primary Scale of Intelligence third edition.	WPPSI III	IQ score
7-16 years	Wechsler Intelligence Scale for Children fifth edition	WISC V	IQ score
Motor development			
2-3 years	Bayley scales of infant and toddler development third edition	Bayley III	Motor test score
2-18 years	Neurologic Examination According to Touwen.	Touwen	Gross Motor Function Classification System
Quality of life			
5-7 years	Pediatric Quality of Life Inventory	PedsQoL	Health related quality of life score
8-12 years	Pediatric Quality of Life Inventory	PedsQoL	Health related quality of life score
Behaviour			
1.5-5 years	Child Behavior Checklist	CBCL	Behaviour test score
6-18 years	Child Behavior Checklist	CBCL	Behaviour test score
Course of infections			
2-18 years	Questionnaire based on 'Richtlijn diagnostiek naar onderliggende aandoeningen bij kinderen met recidiverende luchtweginfecties'		Indication for diagnostic evaluation by immunologist; Yes/No.

Table 2: Overview assessments

Study assessments			
Age group	Name assessment tool	Abbreviation	Outcome
Atopic constitution			
2-18 years	Questionnaire composed in collaboration with allergist ([name]).	(Parent reported)	Allergy
Severity of asthma and hay fever			
6-18 years	Control of allergic rhinitis and asthma test.	CARATkids	CARATkids score

Table 3: Definitions of outcome

Definitions of outcome		(1/3)
Outcome parameter	Definition	
Obstetric medical data		
Pregnancy induced hypertension	De novo hypertension (blood pressure above 140/90 mmHg) after gestational week 20.[26]	

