Intracerebral bleeding	Any bleeding in the cerebral cavity.	
Organ bleeding	Bleeding in any organ located in the thorax or abdomen.	
Postpone bleeding	Postpone bleeding that was noted as sign of bleeding by the caretaker.	
Skin manifestations	Petechiae, purpura or hematoma diagnosed by the caretaker at neonatal period (gynecologist, pediatrician or midwife).	
Neonatal IVIG treatment	Any administration of IVIG after birth.	
Platelet transfusion	Any platelet transfusion.	
Neurodevelopmental impairment		
Cerebral Palsy	Spastic bilateral, spastic unilateral or mixed Classification by European CP Network [19].	
Impaired cognitive or motor development	Score < 70 (2 SD below the mean) as assessed by Bayley Scales of Infant and Toddler Development version 3 (BSID III) [16]	
Bilateral blindness	Blind or partially sighted.	
Bilateral deafness	Needing hearing aids.	

Definitions of outcome		(3/3)
Outcome parameter	Definition	
Secondary outcomes		
Abnormal course or incidence of infections	Need to refer to an immunologist or the need to perform diagnostics based on history taking according to the Dutch guidelines. [23]	
Prevalence of allergies	Parent reported allergy.	
Patient reported anaphylaxis	Serious allergic reaction, requiring urgent medical treatment with epinephrine.	
Poor control of allergic rhinitis	CARAT score of upper airways < 8.[22, 33]	
Poor control of asthma	CARAT score of lower airways < 16.[22, 33]	
Prevalence of eczema	Parent reported eczema.	
Demographic characteristics		
Ethnic origin of the parents	Ethnic origin of mother and father.	
Educational level of the parents	Highest level of graduation of the parents.	
Smoking	Any person living in the household of the child smoking one or more cigarettes a day.	
Day-care visit	When child is in day care at least one day a week.	
Family history (first degree) of allergy, asthma or eczema	Positive when 1 st degree of family members receive daily treatment for asthma or eczema. Or when a family member wears an epinephrine pencil because of a severe allergy.	

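### Allergy, asthma and eczema prevalence, meant to show IVIg side effects, rests on an uncited questionnaire, has no asthma case definition, and is compared with nothing

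*Combined protocol and SAP*

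**What the plan says.** Section 3.2 gives the purpose of the endpoint: "We will also focus on potential long-term side effects of IVIg treatment". Section 9.1.2 lists two outcomes for effects of maternal IVIg on the child's immune system, atopy and infections. For the first it says: "The prevalence of allergies, asthma and eczema will be evaluated by a questionnaire composed in collaboration with an allergist".

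- **Instrument.** Table 2 lists it as "Questionnaire composed in collaboration with allergist", for ages 2 to 18, parent reported, without a reference.
- **Definitions.** Table 3 defines allergy as "Parent reported allergy" and eczema as "Parent reported eczema". For asthma it defines only poor control: "CARAT score of lower airways < 16".
- **Other tool in the same domain.** "The severity and control of the allergic rhinitis will be assessed by the CARATkids questionnaire". Table 2 applies it from age 6, to severity of asthma and hay fever. Children are eligible from age 2 (Section 5.2).
- **Analysis.** Chapter 11 assigns atopy to a secondary analysis in cohort 2, the IVIg-treated children. It lists family history and household smoking as confounders for allergies and asthma. It names the Dutch average as reference for the cognitive score, and nothing for atopy.
- **Earlier study.** Chapter 2 says of a previous follow-up study: "Their conclusions were based on non-validated questionnaires taken by telephone". That criticism concerned behavioural outcome and stands beside a loss to follow-up of about 40%.

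**The concern.** The side-effect question is whether atopy is more frequent after IVIg than it would otherwise have been. Answering it takes a defined case, a measurement whose behaviour is known, and a rate to compare with. The plan is incomplete on all three.

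At stake is one of only two endpoints on immune effects, in a study whose summary says that the long-term safety of IVIg in FNAIT has not been evaluated. A bare percentage could be read as reassuring or alarming, depending on which outside figure a reader sets beside it. The type of instrument is also one that the protocol itself counts as a limitation elsewhere, which invites the same criticism of this result.

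**Working it through.** **1. Tools side by side.** Section 9.1 cites a source for Bayley III, WPPSI III, WISC V, the Touwen examination, PedsQL, the Child Behavior Checklist and CARATkids. It ties the infection questionnaire to a guideline and to published warning signs. The atopy questionnaire is the only tool in Table 2 with no source. CARATkids does not fill the gap, since control of a disease is not its prevalence and the tool starts at age 6.

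**2. Definitions.** Allergy and eczema have no recall period (ever or current) and no diagnostic criterion. Asthma prevalence is an objective in Section 3.2 but has no definition in Table 3.

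**3. Comparison.** In cohort 2 every mother received IVIg. A model within that cohort, adjusted for family history and smoking, contains no treated-versus-untreated contrast. A reference rate or a second group has to come from outside that analysis, and Chapter 11 names neither.

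**4. The plan's own figure.** The only sample size (Section 5.4) is 39 per cohort, for IQ. Inputs: SD 15, difference or margin 7, power 0.80, two-sided 0.05 (cohort 1, sidedness assumed) or one-sided 0.025 (cohort 2). The normal approximation is n = [15 × (1.960 + 0.842) / 7]² = 36.0, rounded up to 37. The noncentral t gives 39, with power 0.811, in both cases. The figure reproduces, but it was not set for prevalence and is a minimum, not a cap.

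**5. Precision at n = 39.** Clopper-Pearson limits are the 2.5% point of Beta(x, n − x + 1) and the 97.5% point of Beta(x + 1, n − x). The counts are hypothetical.

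- 2/39 (5.1%): 0.6% to 17.3%
- 4/39 (10.3%): 2.9% to 24.2%
- 8/39 (20.5%): 9.3% to 36.5%
- 12/39 (30.8%): 17.0% to 47.6%

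**6. Excess detectable against a fixed reference.** Exact binomial test, upper tail at most 0.025, power 0.80. Reference rates are assumed.

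- Reference 5%: at least 6 positives needed; true prevalence about 20%
- Reference 10%: at least 9; about 28%
- Reference 20%: at least 14; about 41%
- Reference 30%: at least 18; about 52%

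For two cohorts of 39, by normal approximation at two-sided 0.05, a rate of 20% in one needs about 50% in the other.

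**7. Reference measured with different items (all inputs assumed).** Observed rate = p × Se + (1 − p) × (1 − Sp), with true p = 0.20 and Se = 0.9:

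- Sp 0.95: 0.18 + 0.04 = 22%
- Sp 0.90: 0.18 + 0.08 = 26%
- Sp 0.80: 0.18 + 0.16 = 34%

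Against an error-free 20% reference, the chance of 14 or more positives in 39 is 3.4%, 11.2% and 46.1% respectively. It would be 1.5% if the instruments agreed. The error can also run the other way: with Se 0.7 and Sp 0.95, the rate reads 0.14 + 0.04 = 18%.

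**The case against.** The strongest reply is that the missing comparison, not the questionnaire, makes the endpoint uninterpretable. Table 2 does not restrict the form by cohort, Section 9.3 sends allergy questionnaires home without restriction, and Section 9.1.3 collects atopic family history across the study groups. Cohort 1 could therefore serve as an internal yardstick on the same form. This stands in part. It shows that a new instrument alone would not help, and the fix below therefore includes the comparison. It does not remove the point, because Chapter 11 states no such contrast.

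The other side is also right that several stronger readings go too far:

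- A reader might infer that no population prevalence exists. The documents show only that none is named and that no norms are given for this questionnaire.
- A reader might infer that the items were invented for this study. The wording is compatible with assembling established items, and the form is not reproduced.
- A reader might infer that the protocol contradicts its own criticism of the earlier study. That criticism was about behaviour, which is measured here with the cited Child Behavior Checklist. The parallel lies only in the type of instrument.
- A reader might infer that item wording shifts the result as much as sampling error does. The documents give nothing on that, and step 7 depends wholly on its assumed error rates.

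On weight, this is a secondary analysis with no test or margin attached, parent report is openly declared, and anaphylaxis does have a concrete definition. All of this limits the seriousness of the point.

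**Conclusion.** The point holds in this form: the atopy prevalence comes from an uncited parent-report questionnaire with no stated validation or norms, asthma has no case definition, and no reference prevalence or comparison group is named. The planned percentage therefore cannot show an excess or its absence. This rests on the text alone and needs no assumption.

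The size is illustrative. It assumes 39 children, reference rates of 5% to 30%, and the error rates in step 7. Under these, only large excesses are detectable (20% against about 41%), and a borrowed rate from different items could give a false excess with a probability of about 3% to 46%. More children than 39 would narrow the intervals, but would supply neither a comparator nor a case definition.

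The change should be made because it is cheap and the endpoint carries a safety question. The primary analysis is not affected.

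**What to change.** - **Section 9.1.2 and Table 2.** Put first, and verbatim, the core asthma, hay fever and eczema items of a validated parent questionnaire that has published population prevalence for the ages it covers. Cite it. Keep the allergist's items as a supplement, for example for food allergy and anaphylaxis, and state their validation status.
- **Table 3.** Define the prevalence of asthma, eczema and allergy from those items, with the recall period.
- **Chapter 11.** Name the comparison: cohort 2 against the published age-specific prevalence, with an exact 95% confidence interval, and descriptively against cohort 1 on the same form.

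**Cost.** About one extra page for parents and a revised form before it is sent out. The form is completed at home, so no extra staff or visit is needed. The documents cannot show which instrument is suitable, and reference data may not cover every age from 2 to 16. Children outside the covered ages would be described only, which reduces the number compared.
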